7.4 Biomechanics

At the baseline and 12-month follow-up visits, we will assess 3D lower-limb biomechanics (VICON) during walking and running, single and double leg drop-jump and single leg hopping. Reflective markers will be placed on the lower-limbs and trunk and participants will be asked to walk and run across force plates in the La Trobe University Gait Laboratory to assess lower-limb kinematics and kinetics. Participants will also drop off a 30cm high step and land on: i) one-leg and ii) two legs.

7.5 Structural Outcomes on MRI

MRIs will be obtained using a 3T scanner (GE) and 16-channel knee coil, on the ACLR knee of all participants at baseline, 4 and 12-month follow-up. Positioning aids will immobilise and support patients laying supine, ensuring consistent, reproducible images. A contralateral knee MRI will also be acquired in a subset of participants without contralateral knee injury/surgery history. Sequences acquired will include proton density weighted fat suppressed sagittal, axial and coronal sequences, and a T2 mapping multi-echo spin-echo sequence. Lake Imaging will provide a radiology report written by a licensed and registered Radiologist with The Royal Australian and New Zealand College of Radiologist

Structural outcomes will be: i) cartilage quality using T2 relaxation time; ii) whole joint morphology using MRI osteoarthritis knee score (MOAKS); and iii) cartilage thickness

Degeneration in cartilage collagen content and orientation in extracellular matrices will be defined by quantitative changes in T2 relaxation times⁹. Post-processing software incorporating automated registration in 3D developed at University of San Francisco, California will be used.

Knee osteoarthritis features (e.g. cartilage, meniscal and bone marrow lesions and osteophytes) will be scored with MOAKS¹⁰ by a trained reader blinded to clinical outcomes. Individual osteoarthritis feature worsening will be defined as increase in the size or depth of lesions as previously established¹¹.

Cartilage thickness will be assessed by segmentation of knee cartilage plates and reported as the mean cartilage thickness over the total area of the subchondral bone.

7.6 Process evaluation

Semi-structured interviews will be conducted on a subset of participants at 4-months and 12-months post commencement of intervention. Interviews will explore beliefs/experiences; knowledge and understanding of interventions received including potential benefits; acceptability and perceived effectiveness of the intervention; and reasons for adhering (or not) to exercise-therapy and education provided. Purposive sampling will be used to recruit interview participants from different sites (including public and private), and participants will be stratified based upon characteristics and outcomes of trial (good outcome; poor outcome). Approximately 30 interviews (15 SUPER; 15 CONTROL) will be conducted for each time-point (or until saturation is reached). Interviews will be audio recorded, transcribed and analysed using Framework Analysis,¹² supported by NVivo software. Re-identifiable (i.e. coded) audio recording transcriptions will be completed by 'Transcription Australia' on their secure, encrypted Australian-based software. Participants will have the opportunity to review the transcripts and edit their responses as appropriate prior to analysis. Following the completion of analysis of this transcription, the audio file associated with the interview will be deleted.

The qualitative coding process will start with a research team member checked transcripts being read for overall understanding, and to identify emergent themes and concepts. An integrated approach will follow two lines of reasoning. First, the data will be coded deductively according to the code structure generated by the interview topic guide. Second, an inductive thematic analysis following a grounded approach will be applied until no new themes emerge. To enhance reliability, the final code structure will then be re-applied to the data independently by a second member of the research team. Any discrepancies will be discussed between the two researchers until a consensus is reached. NVivo computer software will be used to assist the coding process.

Table 1. Overview of outcomes

	Baseline	2 months	4 months	12 months	18 months
Baseline characteristics					
Age	X				
Sex	X				
Education level, health literacy	X				
Employment status	X				
Prior knee injury/treatment	X				
Injury and rehabilitation details	X				
Medication	X				
Family history of osteoarthritis	X				
Patient-reported Outcomes					
Knee injury Osteoarthritis Outcome Score	X	X	X	X	X
EQ-5D	X	X	X	X	X
ACL – return to sport index	X		X	X	X
Tegner Activity Scale	X	X	X	X	X
Tampa Scale of Kinesiophobia	X		X	X	X
Knee self-efficacy scale	X		X	X	X
Global rating of change		X	X	X	X
Anterior knee pain scale	X		X	X	X
Patient acceptable symptoms state	X	X	X	X	X
Health and Labour Questionnaire	X		X	X	X
ACL-QOL	X		X	X	X
Work Limitations Questionnaire	X		X	X	X
Objective Clinical Outcomes					
Height, weight, waist girth	X		X	X	
Hop tests	X		X	X	
One-leg rise	X		X	X	
Knee effusion	X		X	X	
Muscle strength	X			X	
Movement quality	X			X	
MRI Outcomes					
	X		X	X	
Biomechanics					
	X			X	
Semi-structured interviews					
			X	X	

All participants will receive either a fortnightly (during Phase 1) or monthly (during Phase 2) online questionnaire via the secure online platform (REDCap) (or hard copy mailed, or phone call depending on participant preference) to assess sports activity, adherence to exercise-therapy, and any adverse events/other treatment.

8. Data Management

Data will be generated directly from participants. Participants will complete patient reported outcome measures, physical measures, MRI and qualitative interviews. This information collected from each participant will form the basis of the data generated from this project. Participant questionnaires will be stored electronically on a secure electronic data collection server hosted by La Trobe University

(REDCap) or completed on hard copy and uploaded to REDCap/Excel. Physical measures will be recorded on hard copy data collection sheets and uploaded to REDCap/Excel.

All study related documentation will be stored securely in a locked filing cabinet in a locked office at La Trobe University and in electronic files password protected and stored on the La Trobe University research drive (P:) only accessible to the research team. All data will be deidentified with the use of a participant code.

Identifying documents (e.g. consent forms, screening sheets, data linkage files, intervention clinical notes (by treating physiotherapists)) will be securely stored separately from re-identifiable (i.e. coded) data.

At the completion of the study when the specified period of retention has finished, identifiable data will be disposed in a secure and safe manner in accordance with the Australian Code for the Responsible Conduct of Research, the University Records and Archives Management Policy, and the Victorian Public Records Act 1973.

As recommended by the NHMRC Open Access Policy, non-identifiable data will be made available to be used in future related research upon reasonable request to the research team. CI [name] will have ongoing custody of data and research outputs, including any intellectual property ownership. Participant privacy will be protected when data are made available by making the data entirely non-identifiable. It will not be possible to identify individual participants from this data.

9. Data Analysis

For the primary hypothesis, generalised linear models (with baseline value as a covariate and treatment condition and referral source [public vs private] as fixed factors) will be used to evaluate the treatment effect on KOOS₄ at 4 months ($p < 0.05$). A generalised linear model utilising repeated measures at all time-points (for 12 and 18-month secondary hypotheses) will allow non-biased estimates of treatment effect in the presence of any potential missing cases, providing data are missing at random. However, a sensitivity analysis to missing data will also be carried out using multiple imputation to ensure there are no unexpected biases. This approach also permits adjustment for differences between groups in potential confounders at baseline (age, sex, BMI, duration between injury and surgery). A confidence interval excluding 10 points or more on the KOOS₄ will be interpreted as a lack of a clinically meaningful difference.

For secondary binomial outcomes (e.g. cartilage defect worsening assessed with the MOAKS), mixed-effect logistic regression models will be used to assess the effect of treatment. Treatment will be included as a fixed factor and covariates will also be included to adjust for potential confounding factors. Estimates of association will be presented as unstandardized regression coefficients and risk ratios, together with 95% CIs.

All randomised participants will be included in the intention to treat analysis and in the safety analysis. Per protocol and as treated analyses will be performed for primary and secondary outcomes by a statistician blinded to group allocation.

10. Economic evaluation

The primary measure for the economic evaluation for each trial arm will be the cost (healthcare system perspective) per Quality Adjusted Life Year (QALY) derived from EQ-5D assessments. Program costs of delivering each intervention will be summarised and included in estimating average costs per patients treated in each arm of the study. Cost estimates will be calculated from treatment resource use, healthcare resource utilisation including co-interventions for knee symptoms (e.g. medicines, complementary treatments, and hospital presentations). These costs will be collected from several sources for corroboration and analysis up to the 18-month primary time horizon. Participant log-books and monthly questionnaires will be used, alongside data from the Medicare and Pharmaceutical Benefits Scheme databases (rebated and out-of-pocket costs).

The EQ-5D is a reliable and valid measure of health-related QoL recommended for economic evaluations⁵, and suitable for use in people following ACLR. It will be administered at baseline, 4, 12, and 18 months to permit calculation of QALYs using an area under the curve approach. A utility score will be generated from the EQ-5D questionnaire, which ranges from 1 (perfect health) to -0.59 (severe problems on all 5 domains).

Indirect costs (e.g. lost work days) that are not accruable to healthcare costs will be reported, but not included in the primary economic evaluation from the healthcare system perspective. Healthcare utilisation data will be costed at market rates (e.g. using Medicare and PBS costing). A trial-based incremental cost-effectiveness ratio (ICER) will estimate the incremental cost-effectiveness of the treatment approaches consistent with the trial arm comparisons outlined in the data analysis.

11. Fidelity Assessment

Fidelity assessment will be undertaken annually at each physiotherapy site where at least 5 participants have been treated to ensure key components of the intervention are delivered, adherence to the protocol throughout the trial. Files will be audited, and routine interventions will be observed at least annually.

12. Intervention adherence, adverse effects and co-intervention

In both SUPER and CONTROL groups, adherence will be collected in a number of ways: i) via a secure online app (e.g. Physitrack™) and/or self-reported paper log-books as preferred; and ii) via a monthly physical activity/exercise-therapy questionnaire completed via a secure online platform (REDCap). For participants randomised to the SUPER group, adherence will also be collected via attendance at physiotherapy supervised group/1:1 sessions.

To increase adherence, we will provide opportunity for participants to attend physiotherapy clinics at various locations, to minimise transport burden, and telerehabilitation (via Zoom) is available if needed. We will also train treating physiotherapists in the use of motivational interviewing techniques to assist adherence and retention. Participants from both SUPER and CONTROL groups will have their travel costs to attend baseline and follow-up assessments remunerated.

Any adverse events and serious adverse events will be recorded via a fortnightly (during Phase 1) and monthly (during Phase 2) questionnaire by asking participants if they have experienced any illness or injury that has affected their ability to function normally, and whether they have seen any health care professional (apart from physiotherapy as part of the SUPER intervention). Furthermore, open probe questioning will enquire about possible adverse events at each of the follow-ups. The MBS data obtained as part of cost-effectiveness analysis at final follow-up will also be checked for any possible adverse events.

An adverse event is defined as any undesirable experience during follow-up causing participants to seek medical treatment (e.g. general practitioner). A serious adverse event is defined as any undesirable event/illness/injury classified as having the potential to significantly compromise clinical outcome or result in significant disability or incapacity, those requiring inpatient or outpatient hospital care, to be life-threatening, or to result in death. Adverse events will be categorised into index knee or other sites and will be provided to the data safety monitoring committee for assessment.

In both randomised groups, co-interventions will be monitored with a “other treatment log-book” and via a fortnightly (during Phase 1) and monthly (during Phase 2) questionnaire regarding other treatments.

13. Sample Size

A total of 184 participants (equally allocated) will enter this two-armed parallel-design trial. For the primary outcome of KOOS₄, the overall effect size for exercise-therapy on self-reported pain and disability is moderate (0.50)¹³. With this effect size, to achieve 85% power at a two-sided 0.05 significance level on the KOOS₄, 146 participants are required. To account for an estimated 20% drop-out, we will recruit 184 participants. This sample size will be sufficient to detect a minimal important change (MIC) in KOOS₄ of 9-points (with standard deviation of 15)^{14 15}. If the intended sample size is not reached at 30 months after recruitment commencement, the inclusion of participants will stop at 160, which will ensure a power of 80%, anticipating 20% loss to follow-up.

Including a minimum of 160 participants will also provide $\geq 90\%$ power to detect a statistically significant difference ($\alpha=0.05$) on the secondary outcome of cartilage quality on MRI (change in cartilage T2 relaxation time) between SUPER and CONTROL groups (anticipated effect size of 0.59)¹⁶.

14. Privacy and Confidentiality

Participants will be made aware that re-identifiable (i.e. coded) data will be used for this study. All data will be reported in a re-identifiable and aggregated format so that individuals will not be able to be identified. All records will have an identifying number only and will not include the names or contact details of participants. The code linking participant names and contact details will be kept separately in a locked filing system. All data will be stored according to La Trobe University and hospital policies; these comply with NHMRC guidelines for conduct of research (<http://www.nhmrc.gov.au/publications/synopses/e72syn.htm>). Participants will be informed that if they choose to withdraw from the trial that personal health information already collected will be

retained, unless an explicit request to the contrary, to ensure that the results of the research project can be measures properly.

Data obtained at hospital sites during the screening process on the participant screening sheet will be scanned and transferred to the Trial Coordination Site (La Trobe University) by e-mail. Data will be electronically shared using organisational email addresses only. Electronically shared data will be stored in electronic password protected folders on the La Trobe University research drive (P:) only accessible to the research team. Electronic data transfer will allow for timely data collection.

Re-identifiable (i.e. coded) linked data provided by the Medicare and Pharmaceutical Benefits Scheme databases will be submitted into, and maintained within, a secure data research storage system. Only approved members of the research team will have access to these data and it will be used solely for the purposes of this project.

15. Reporting Project Results

Reports containing the results of the project will be provided to the NHMRC who provided funding, and a lay summary report will be available for study participants on request. The results will be reported in peer-reviewed publications and presented at scientific conferences. Only aggregate data will be reported. Individuals named as site investigators on the Clinical Trial Research Agreements (CTRAs) and/or *Health Service* Research Governance authorisations will be recognised in the acknowledgments section of all publications arising from the study that include participants recruited from *Study staff, Health Service or Institution* unless they elect not to be acknowledged. Private orthopaedic surgeons who have at least one of their patients included in the study will also be recognised in the acknowledgments sections of all publications arising from the study unless they elect not to be acknowledged.

16. Funding

The study has been supported by a NHMRC Project Grant (APP1158500; 2019-2024)

17. Potential Significance

Despite the best efforts of primary prevention strategies, ACL injuries and subsequent reconstructions in young Australians have increased ~200% over the past 20 years (Medicare Data 1994-2016). These young adults are at high risk for persistent pain and symptoms, impaired QoL and early-onset knee OA. This underscores an urgent need for secondary prevention strategies to prevent post-traumatic knee osteoarthritis - an epidemic of young people with old knees.

This study will evaluate the world's most comprehensive education and exercise-therapy intervention for people with post-traumatic knee osteoarthritis, which is: (i) developed on the foundation of our substantial prior work in this field; (ii) informed by patients and clinicians; (iii) feasible to implement; and (iv) underpinned by a strong scientific rationale to reduce the burden for those at risk of post-traumatic osteoarthritis. The SUPER intervention has the potential to reduce the symptomatic burden, be cost-

effective, and slow the structural disease trajectory. Our trial fills an urgent need for clinical trials evaluating musculoskeletal conditions in Australia.

By improving patient outcomes beyond the unacceptable levels currently experienced, we will enable greater participation in work, physical, family and social activities. These improvements in outcomes are integral to a productive and available Australian workforce and facilitating healthy ageing.

By establishing the cost-effectiveness, we will demonstrate the benefits of our best-practice intervention to inform future models of osteoarthritis care. Changing healthcare funding models is beyond the scope of this proposal, but cost-effectiveness data will contribute to evidence-informed resource allocation.

If we succeed in reducing the rates of osteoarthritis worsening, we will be the first in the world to modify the trajectory of post-traumatic structural osteoarthritis disease with an exercise-therapy intervention. Our results will have potential for longer term outcomes, including reducing the risk of early joint replacement. We will help to keep these young adults, who are typically active and healthy prior to injury, from becoming major participants in our future health care system.

This project has the potential to transform the research and practice landscape of knee injury, ACLR and osteoarthritis rehabilitation. Optimising management to achieve better outcomes and curtail the rapid trajectory of post-traumatic knee osteoarthritis will reduce the formidable personal and health care expenditure burden currently associated with this common condition.

18. References

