5.5 Fortnightly/Monthly questionnaires

All participants will receive either a fortnightly (during Phase 1) or monthly (during Phase 2) online questionnaire via the secure online platform (REDCap) (or hard copy mailed, or phone call depending on participant preference) to assess sports activity, adherence to exercise-therapy, and any adverse events/other treatment.

5.6 4-month follow-up assessment

All participants will be re-assessed for functional, patient-reported and MRI outcomes at the completion of Phase 1 of the trial (4-months post-baseline: primary outcome point for KOOS₄) at Lake Imaging Specialist and Research Centre, North Melbourne. Patient-reported outcomes will be completed via the secure online platform (REDCap) (or hard copy mailed if preferred), and all functional measures will be assessed by the blinded assessor.

5.7 12-month follow-up assessment

All participants will be reassessed at the completion of Phase 2 at 12-months post-baseline both at La Trobe University (functional, patient-reported outcomes) and Lake Imaging Specialist and Research Centre, North Melbourne for MRI.

5.8 18-month follow-up assessment

All participants will be reassessed for patient-reported outcomes at 18-months post-baseline via the secure online platform (REDCap) (or hard copy mailed if preferred). Participants do not need to attend the 18-month assessment in person as only patient-reported outcomes (online or post) will be assessed.

6. Interventions

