6.1.1 Exercise-therapy component

The SUPER intervention is split into two main phases. In Phase 1 (0-4 months), all participants randomised to the SUPER intervention, will receive the same duration and frequency of exercise-therapy and education (2 x weekly supervised sessions and 1 x weekly unsupervised session at gym/home, depending on individual preference) (Figure 3). Supervised physiotherapy-led sessions (either group or 1:1) will be 1-hour duration. The Phase 2 intervention will depend on whether predefined criteria are met at the 4-month follow-up assessment (Figure 3).

For participants meeting all criteria, Phase 2 will involve ongoing unsupervised exercise-therapy sessions (gym/home), with the option of booster physiotherapy sessions as required. If all criteria are not met, Phase 2 will involve ongoing once per week supervised exercise-therapy. Once all criteria are met, participants will continue exercise-therapy sessions at gym/home with booster sessions as required.

Participants will be contacted via phone at 2 monthly intervals to increase adherence, with the option of a second opinion by a member of our clinical expert physiotherapy team if the SUPER treatment is failing to facilitate improvement, or adherence is low (Figure 3). This approach of including second opinion reflects real-world clinical care. All participants in the SUPER intervention will be provided with a membership to a local gym to encourage unsupervised exercise-therapy adherence during Phase 2. Exercise options/progressions will be provided to the treating physiotherapists in a treatment manual at the initial physiotherapy training session. The specific exercises and education intervention will be tailored to each participant to match their individual preferences, goals and clinical presentation (e.g. strength, pain severity, personal, sporting, work and functional needs). The three key components (lower-limb and trunk muscle strength; movement quality; and sport- or activity-specific retraining) have phases of increasing difficulty. The physiotherapist will supervise and progress exercises based on defined criteria (perceived difficulty, minimal pain), and provide feedback during each visit. Equipment (e.g. TheraBand, weights) will be provided for participants to be able to complete exercises at home.

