6.2 Control Intervention

Minimal Intervention CONTROL

Participants randomised to the CONTROL intervention (i.e. activity monitoring program) will receive a “best-practice guide” booklet and a face-to-face appointment (at baseline assessment) with a registered physiotherapist with ≥ 3 years clinical experience (not involved in treating SUPER participants). The physiotherapist will explain elements of the booklet and answer any questions. The booklet was produced based on the information to patients provided by orthopaedic surgeons participating in this trial, together with exercise prescription guidelines and best-available evidence for exercises and education following ACLR. Examples of exercises to strengthen specific lower-limb and trunk muscles, and methods to safely progress these are included, as well as education regarding monitoring and managing symptoms and safe return to sport.

Participants randomised to the CONTROL intervention may also contact the physiotherapist by phone to ask questions/get further clarification. The physiotherapist cannot volunteer information extending the scope of the booklet.

7. Study Outcomes

Blinded outcome assessment will occur at 4 months (primary outcome KOOS₄), 12 and 18 months. 12 and 18 months is the primary time-horizon for the knee structure (MRI) and economic evaluation, respectively. Fortnightly (Phase 1) and monthly (Phase 2) collection of co-interventions, adherence, adverse events, and physical activity will be completed via short questionnaires online or via paper log-books.

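### Months 12 to 18 of the 18-month economic evaluation have no scheduled participant-reported resource-use questionnaire, and Section 10 and Table 1 disagree on a 2-month EQ-5D

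*Protocol*

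**What the plan says.** **Horizon and cost sources.** The 18-month horizon appears in the cost-effectiveness hypothesis (Section 2.2), in Section 7 and in Section 10. Section 10 states: "These costs will be collected from several sources for corroboration and analysis up to the 18-month primary time horizon". The costs include "healthcare resource utilisation including co-interventions for knee symptoms (e.g. medicines, complementary treatments, and hospital presentations". The sources are given as: "Participant log-books and monthly questionnaires will be used, alongside data from the Medicare and Pharmaceutical Benefits Scheme databases (rebated and out-of-pocket costs".

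**Questionnaire schedule.** Section 5.5: "All participants will receive either a fortnightly (during Phase 1) or monthly (during Phase 2) online questionnaire". Section 7 describes "Fortnightly (Phase 1) and monthly (Phase 2) collection of co-interventions, adherence, adverse events, and physical activity", online or by paper log-book. The note under Table 1 and Section 12 use the same two-phase schedule. Section 6.1.1 fixes the first phase ("In Phase 1 (0-4 months), all participants randomised to the SUPER intervention") and Section 5.7 the end of the second: "All participants will be reassessed at the completion of Phase 2 at 12-months post-baseline".

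**EQ-5D.** Section 10: "It will be administered at baseline, 4, 12, and 18 months to permit calculation of QALYs using an area under the curve approach". Table 1 marks EQ-5D in all five of its columns: baseline, 2, 4, 12 and 18 months.

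**The concern.** The economic section relies on a monthly participant report over a window that the schedule sections do not cover. If sites follow Sections 5.5, 7 and 12, participants are sent no resource-use form after month 12, while the economic analyst expects one up to month 18. Participant-reported care that was not recorded at the time cannot be restored by analysis, so this is a matter for the protocol's schedule and not one that a later analysis plan can repair. At stake is the completeness of the cost side of a stated secondary hypothesis, in both arms, and the cross-checking of sources that Section 10 promises.

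The EQ-5D mismatch is a smaller, separate matter. Section 10 and Table 1 cannot both be right on whether the instrument is given at month 2. That time lies in the middle of Phase 1, when SUPER participants have two supervised sessions a week. Without it, the utility path from baseline to month 4 is a straight line by assumption.

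**Working it through.** The plan gives no figure to reproduce here. The check compares schedules and then works out the QALY weights.

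**Step 1: what covers months 12 to 18?**

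| Source | What the protocol says | Months 12 to 18 |
|---|---|---|
| Periodic questionnaire | Fortnightly in Phase 1, monthly in Phase 2 (5.5, 7, note to Table 1, 12); Phase 2 complete at month 12 (5.7) | None scheduled |
| Other-treatment log-book | Section 12 gives no end date; Section 7 ties log-book collection to Phases 1 and 2 | Unclear |
| 18-month assessment | Patient-reported outcomes only (5.8); in Table 1 the nearest instruments are the Health and Labour and Work Limitations Questionnaires, which concern productivity, and Section 10 keeps indirect costs out of the primary evaluation | No healthcare resource-use instrument |
| Medicare/PBS linkage | Named in Section 10; Section 12 has the Medicare data obtained at final follow-up | Available for what those schemes record |

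Share of the horizon without a scheduled questionnaire: (18 - 12)/18 = 33%.

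**Step 2: QALY weights.** With the trapezoid rule and time in years, each interval contributes its length times the mean of its two end utilities.

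| Schedule (months) | Weights | Sum |
|---|---|---|
| 0, 4, 12, 18 | 0.1667, 0.5000, 0.5833, 0.2500 | 1.5 |
| 0, 2, 4, 12, 18 | 0.0833, 0.1667, 0.4167, 0.5833, 0.2500 | 1.5 |

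Month 2 carries 0.1667/1.5 = 11% of the weight, half taken from baseline (0.1667 to 0.0833) and half from month 4 (0.5000 to 0.4167). Subtracting the first schedule from the second, the change in a participant's QALY is

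u2/6 - u0/12 - u4/12 = (u2 - (u0 + u4)/2)/6.

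It is zero if utility moves in a straight line from baseline to month 4. Assumed departures from that line of 0.02, 0.05 and 0.10 give 0.0033, 0.0083 and 0.0167 QALY.

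**Step 3: illustrative between-group paths.** These utility differences at months 0, 2, 4, 12 and 18 are assumptions, as the protocol gives none.

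| Assumed path | With month 2 | Without | Shift | Shift / figure with month 2 |
|---|---|---|---|---|
| 0, 0.04, 0.05, 0.05, 0.05 | 0.0692 | 0.0667 | +0.0025 | +3.6% |
| 0, 0.05, 0.05, 0.03, 0.02 | 0.0517 | 0.0475 | +0.0042 | +8.1% |
| 0, 0.01, 0.05, 0.05, 0.05 | 0.0642 | 0.0667 | -0.0025 | -3.9% |

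The second shift, for example, is (0.05 - 0.025)/6 = 0.0042. An early gain raises the incremental QALY once month 2 is used, and a slow onset lowers it.

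**The case against.** **Costs.** No sentence says that the questionnaires stop at month 12. That end date comes from reading the phase wording together with Section 5.7, and Section 10 could be taken to mean that they run to month 18. This stands as a caution, but Section 10 would then conflict with four other places, so a correction is needed on either reading.

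A reader might infer that participants' costs are measured over 12 months and QALYs over 18, so that the ICER compares different windows. The documents do not support that. Linked data reach the final follow-up and are said to include rebated and out-of-pocket costs, program delivery costs are counted separately, and the log-book may continue. Costs therefore run to 18 months, with some components less completely captured in the last six. Nor do the documents show that any later saving in care would fall in that window. Equally, one cannot rely on recall at month 18 to fill the gap: no look-back for resource use is described, and the open questioning at follow-ups in Section 12 concerns adverse events.

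**EQ-5D.** It is tempting to say that a collected value is thrown away. Section 10 does not say so; it lists administration times that omit month 2, and Sections 5 and 7 describe assessments at 4, 12 and 18 months only. In favour of Table 1, month 2 has its own column there and is marked for several instruments. The conflict is over whether the measurement takes place, and it has to be settled before one can speak of leaving anything out.

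**Conclusion.** The point holds as two schedule inconsistencies of unequal weight.

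- **Resource use (the weightier).** As written, one third of the economic horizon has no scheduled participant-reported resource-use questionnaire. Capture is incomplete for self-reported components such as complementary treatments, and the planned corroboration between sources is lost for those months. This assumes that the phase wording means what it says and that linkage does not record every item listed in Section 10; the protocol does not set out which items linkage would miss.
- **EQ-5D (minor).** Section 10 and Table 1 contradict each other on month 2. The weight at issue is 11% of the QALY total. The figures of about -4% to +8% of incremental QALYs come from assumed paths and change sign with the path. They are not an expected effect and do not show bias in the ICER in either direction.

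The primary analysis of KOOS₄ is not affected.

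**What to change.** (a) In Sections 5.5, 7 and 12, continue a short resource-use and other-treatment questionnaire to month 18 in both arms, or state explicitly that the other-treatment log-book runs to month 18 and how it is collected. Monthly forms would cost up to six more short forms per participant; extending the log-book needs fewer forms but a defined return at month 18.

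(b) Reconcile Section 10 with Table 1. As Table 1 schedules the 2-month EQ-5D, list baseline, 2, 4, 12 and 18 months in Section 10 and use all five in the area under the curve. If the 2-month measurement is taken as Table 1 shows, this adds no data collection and is an edit to one sentence. If it is not taken, Table 1 needs the correction instead.
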